From raw data of individual teeth, each patient received a global index of periodontal disease, gingival index, and plaque for each visit. The global index for each of these measurements was found by dividing the sums of patient probing depth, gingival index, and plaque findings collected for each tooth by the number of teeth assessed. Over the three assessment periods, global scores of probing depth, gingival index, and plaque were collected for the first and last visits with probing depth scores not collected during the second visit. These outcomes are measured as individual slopes of responses across the three observation visits. The slope represents the rate of change.

The overall view of the response of each measure to the treatment group is summarized in the following general linear model Table 2. Table 3 shows the cell statistics for the slopes of each condition and outcomes reported in Table 2.

Table 2. Master table of variance components attributable to treatment on individual rates of change on the three measures: probing depth, gingival index, and plaque.

Source	Variable	Type III SS	df	MS	F	Sig.
Group	Slope of probing depth, time 1 to 3	0.125	1	0.125	1.191	0.28
	Slope of gingivitis index, time 1 to 3	0.485	1	0.485	11.748	0.001
	Slope of plaque score, time 1 to 3	4.019	1	4.019	69.751	0.000
Error	Slope of probing depth, time 1 to 3	5.75	55	0.105		
	Slope of gingivitis index, time 1 to 3	2.27	55	0.041		
	Slope of plaque score, time 1 to 3	3.169	55	0.058		
Total	Slope of probing depth, time 1 to 3	6.519	57			

Slope of gingivitis index, time 1 to 3	6.135	57
Slope of plaque score, time 1 to 3	18.861	57
Corrected Total	Slope of probing depth, time 1 to 3	5.875
	Slope of gingivitis index, time 1 to 3	2.755
	Slope of plaque score, time 1 to 3	7.187
	R Squared = .021 (Adjusted R Squared = .003)	
	R Squared = .176 (Adjusted R Squared = .161)	
	R Squared = .559 (Adjusted R Squared = .551)	

Table 3. Details of cell statistics for analysis described in Table 2.

Descriptive Statistics					
	N	Minimum	Maximum	Mean	Std. Deviation
Probing depth at time 1	57	2.04	4.63	2.71614	0.432843
Probing depth at time 3	57	0	4.42	2.50351	0.804056
Gingivitis index at time 1	57	1.41	2.23	1.97158	0.172065
Gingivitis index at time 2	57	0	2	1.71754	0.364095
Gingivitis index at time 3	57	0	1.92	1.48456	0.451688
Plaque score at time 1	57	1.47	3.54	2.67895	0.555475
Plaque score at time 2	57	0	3.11	2.19614	0.596444
Plaque score at time 3	57	0	2.92	1.77386	0.618124

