Slope of probing depth, time 1 to 3	57	-1.47	0.015	-0.10632	0.323886
Slope of gingivitis index, time 1 to 3	57	-0.99	-0.03	-0.24351	0.221807
Slope of plaque score, time 1 to 3	57	-1.53	-0.045	-0.45254	0.358255
Valid N (listwise)	57				

Global Probing Depths (GPD)

Global probing depth (GPD) collected at the first visit did not differ significantly between groups; control group's (Group A) initial GPD was 2.76 (SEM = 0.092) interval, and 2.68 (0.071) for test group (Group X), a non-significant statistical difference ($p = 0.48$).

Neither did the GPD score differ between final visits of control group (Group A) (GPD = 2.64 (0.130) and test group (Group X) (GPDI = 2.37, (0.166), $t = 1.27$, $df = 55$, $p = 0.28$. Nonetheless, the GPD decreased significantly for control group (Group A), ($p = 0.028$; for X, $p < 0.001$) for both groups, but the group decreases were not significantly different from each other. Both mouthwashes reduced probing depth similarly.

The key signal of treatment effectiveness is a statistically significant treatment-by-time interaction, where improvement over time is greater for one treatment than another. Nearly parallel lines in Figure 2 and statistical testing indicated no appreciable and significant treatment-by-time interaction for GPD (See Figure 2, Figure 3).

Figure 2. Interaction plot showing that group assignment did not interact with time for probing depth.

[figure not shown]

Figure 3. Boxplots of probing depth results from treatment by control group (Group A) and test group (Group X). Probing depth was not affected differentially by the mouthwash treatments. Both conditions reduced probing depth slightly but not statistically significant.

Global Plaque Score

Control group (Group A) and test group (Group X) differed significantly in global plaque score (GPS) at initial assessment, requiring an additional analysis of covariance to confirm that a significant time by treatment interaction was not an artifact from the initial difference in GPS (See interaction plot, Figure 4, detailed in Figure 5). The test group's (Group X) initial average GPS was 3.00 (SEM = 0.071) versus 2.35 (0.097) for the control group (Group A), a significant difference ($t = -5.45$, $df = 50$, $p < 0.001$). At assessment 3, the last observation, the test group's (Group X) GPS (1.57, SEM = 0.110) was significantly lower than that for the control group (Group A); GPS = 1.98 (0.110), $t = 2.633$, $df = 55$, $p = 0.011$.

[figure not shown]

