Figure 8. No differential effects of mouthwashes on probing depth between implant and non-implant sites. Both groups showed only slight decreases in probing depth. Note that in control condition (rinse A), probing depth was higher for the implant group at baseline.

Implants and Gingival Index

Implant versus normal oral sites also showed a significant main effect ($F = 79.0$, $df = 1$, $p < 0.001$) indicating more and faster gingival index improvement in test group (Group X) for both implant and non-implant sites. Test group (Group X) implants decreased in gingival index scores by 83% while implants in control group (Group A) decreased by 57%. The non-implant sites for control group (Group A) decreased by 23% and for test group (Group X) by 50%. The rate of change was faster for test group (Group X) implants than for control group (Group A) and faster than test group (Group X) non-implant sites. Test Treatment (rinse X) members' implants decrease in gingival index measured 26% versus 19% for those in control group (Group A).

[figure not shown]
Table 6 indicates a strong and statistically significant difference between implant and non-implant sites between and within groups – over time. Figure 9 illustrates the higher gingivitis index in test group (Group X) and greater and faster decrease of gingivitis in test group (Group X).

Table 6. Summary results of general linear model of gingival index measures.

Tests of Between-Subjects Effects

Gingivitis					
Source	Type III Sum of Squares	df	Mean Square	F	Sig.
Intercept	1207.001	1	1207.001	11073.258	0.000
implant	9.949	1	9.949	91.274	0.000
group	9.177	1	9.177	84.187	0.000
implant * group	8.613	1	8.613	79.021	0.000
Error	11.118	102	0.109		

Figure 9. Significant differential effects of mouthwashes on gingival index at implant sites. Both groups showed significant decreases in plaque, but the test group (Group X) reduced gingival index scores more and at a faster rate. Note the difference in gingival index scores at the beginning of the trial.

Implants and Plaque

Plaque scores (PS) for both implant and non-implant plaque scores were higher in the test group (Group X) (2.99 (0.071)) than in the control group (Group A) (2.35 (0.100)) at the first visit, $t = 5.45$, $df = 55$, $p < 0.001$. As with gingival index, PS decreased more for test group (Group X) patients (-0.799 (0.109)) than for control group (Group A) (-0.156 (0.064)) in both implant and non-implant sites, $t = 5.75$, $df = 55$, $p < 0.001$.

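### Implants and Plaque gives what are, to rounding, the whole-mouth baseline scores as holding at implants, against Table 1, and reports plaque decreases with no visit that are probably whole-mouth Day 14 changes

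*Combined protocol and SAP*

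**What the plan says.** Under Implants and Plaque, the baseline sentence reads "Plaque scores (PS) for both implant and non-implant plaque scores were higher in the test group (Group X) (2.99 (0.071", with 2.35 (0.100) for control, t = 5.45 and df 55. The next sentence says that plaque decreased more for test "patients (-0.799 (0.109)) than for control group (Group A) (-0.156 (0.064)) in both implant and non-implant sites", with t = 5.75 and df 55. It names no visit.

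Under Global Plaque Score, the test group's "initial average GPS was 3.00 (SEM = 0.071) versus 2.35 (0.097) for the control group (Group A", with t = -5.45 and df 50. The global changes to the last visit are -1.43 in test and 0.365 in control. The latter is printed without its minus sign, since the control score falls from 2.35 to 1.98.

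Table 1 separates the site types. Baseline plaque at implants is 2.84 (0.057) in test and 2.77 (0.115) in control; at non-implanted teeth it is 2.99 (0.078) and 2.32 (0.101).

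The text after Table 7 gives implant-site slopes of -0.463 (test) and -0.151 (control). Table 7 gives the implant-by-group test.

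**The concern.** The indication is peri-implant mucositis, and the Conclusions claim a preferential benefit at implant sites. This is the section that should support the claim for plaque. Its first comparison reports an implant baseline imbalance that Table 1 contradicts. Its second gives a change with no visit, under an implant heading, with degrees of freedom that do not belong to the implant file. A reader may plan covariate adjustment, or worry about regression to the mean, for an implant imbalance that Table 1 does not show. The same reader may take the printed decreases as the three-month effect at implants.

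**Working it through.** **Inputs.** Means and SEMs are those quoted above. Table 3 (global file, N = 57) gives mean plaque of 2.67895 at time 1, 2.19614 at time 2 and 1.77386 at time 3.

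**Arm sizes in the global file.** The implant counts in the Patients text sum to 18 + 9 + 2 = 29 for test, which leaves 57 - 29 = 28 for control. As a check, solving the Table 3 means for the test-arm size gives 57 x (2.67895 - 2.35)/0.65 = 28.9 at baseline and 57 x (1.98 - 1.77386)/0.41 = 28.7 at the last visit. The split is partly inferred, because the control counts printed in the same text sum to 11 + 13 + 2 + 1 = 27.

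**Step 1: reproduce t = 5.45.** From the global scores, (3.00 - 2.35)/sqrt(0.071² + 0.097²) = 0.65/0.1202 = 5.41 on about 50 df (Welch). The pooled version is 5.43 on 55 df. Both match 5.45 within rounding and account for both printed df, 50 and 55. The rounded inputs printed under Implants and Plaque give 5.25 pooled. The two sets differ by 0.01 in a mean and 0.003 in a SEM.

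**Step 2: the same test by site type, from Table 1.**
- Implants: (2.84 - 2.77)/sqrt(0.057² + 0.115²) = 0.07/0.1284 = 0.55, p = 0.59.
- Non-implanted teeth: (2.99 - 2.32)/sqrt(0.078² + 0.101²) = 0.67/0.1276 = 5.25, p < 0.001.

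**Step 3: degrees of freedom.** A two-arm test with 55 df has 57 patients, the N of Table 3. The implant file has 27 + 26 = 53 patients in Table 1. Table 7's error df of 102 agrees: 102 + 4 = 106 rows, or 53 patients with two site types each. A two-arm comparison there would have 51 df. The between-arm implant comparison under Implants and Probing depth is printed with 52 df, which is not exactly 51 but is not 55 either.

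**Step 4: which interval the decreases fit.** Weighted mean: (29 x -0.799 + 28 x -0.156)/57 = -0.4831.

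| Whole-mouth interval (Table 3) | Change |
|---|---|
| time 1 to 2 | 2.19614 - 2.67895 = -0.4828 |
| time 2 to 3 | 1.77386 - 2.19614 = -0.4223 |
| time 1 to 3 | 1.77386 - 2.67895 = -0.9051 |

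Time 2 is Day 14. Other arm sizes give -0.489 (29 and 27), -0.478 (27 and 27) and -0.471 (26 and 27). All are still nearest the Day 14 change. By arm, the whole-mouth Day 90 changes are 1.57 - 3.00 = -1.43 and 1.98 - 2.35 = -0.37, far from -0.799 and -0.156.

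**Step 5: t for the decreases.** (0.799 - 0.156)/sqrt(0.109² + 0.064²) = 0.643/0.1264 = 5.09 (pooled 5.04). Allowing for rounding of the SEMs, the most it can reach is about 5.11. The text states 5.75. All give p < 0.001.

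**Step 6: what the implant slopes would imply.** The mean global slope, -0.4525, is half the time 1 to 3 change, so the global slopes are per visit interval. If the implant slopes are too (an assumption), the implant changes to Day 90 are 2 x -0.463 = -0.926 and 2 x -0.151 = -0.302, a difference of 0.624.

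**The case against.** The baseline error is hard to defend, but four points can be made about the rest.

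- *Day 14 is inferred.* The row "Plaque score at time 2" in Table 3 is pooled over arms, and Day 14 plaque is nowhere printed by arm. The match is one equation with partly inferred weights. No implant or non-implant change is printed that could exclude another origin. This stands: a reader might conclude that the figures are proven not to be implant changes, and the documents do not go that far.
- *The wording may mean a combined score.* Both sentences refer to implant and non-implant sites together. This stands in part: the decreases are not presented as implant-only or as three-month values. It does not rescue the baseline sentence, which still asserts a difference at implants.
- *The section does contain implant results.* The slopes and Table 7 are implant-specific, and Table 7's df fits the split file. So a reader would be wrong to infer that no implant plaque evidence is given. What is missing is an implant mean change with its SE and visit.
- *The effect on the conclusion may be small.* Under the per-visit assumption the Day 90 implant difference is about 0.62, close to the printed 0.64. Against the whole-mouth Day 90 difference (1.43 - 0.37 = 1.06), the printed figure understates the test rinse. The plaque statements in the Conclusions cite the ANCOVA, difference scores and slopes. Nothing shows that they rest on these two sentences, so the documents do not support a claim that the mislabelling creates or inflates the implant benefit.

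**Conclusion.** The baseline comparison is wrong as written. It is the whole-mouth comparison to rounding, and Table 1 contradicts it at implants (gap 0.07, not 0.64), with a real difference only at non-implanted teeth. This part rests only on Table 1 being correct.

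The decreases lack a visit and carry the global file's df. They are probably whole-mouth Day 14 changes, which is a strong inference that depends on the 29/28 split and needs confirming in the data. The t of 5.75 is not reproducible, but the correction does not alter significance.

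Two features of the source tables limit what can be corrected from the page. Table 1's test row (26 patients, 39 implants) disagrees with the Patients text (42 implants, and counts summing to 29 patients). Table 3 shows minima of 0 for plaque at times 2 and 3, and for whole-mouth probing depth at time 3. That suggests, without proving it, that missed visits were entered as zero.

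**What to change.** 1. Reconcile the patient and implant counts in Table 1 with the Patients text, and check whether the zeros at times 2 and 3 in Table 3 are real scores or missing visits.
2. Then regenerate from the implant/non-implant file, without copying Table 1, the baseline, Day 14 and Day 90 plaque means and changes by arm and site type, each with SE, n, df and visit.
3. Reword the baseline sentence to say that the arms differed at non-implanted teeth but not materially at implants, if the regenerated values confirm Table 1.
4. Label -0.799 and -0.156 by site and visit. If the file shows that they are whole-mouth Day 14 changes, move them to Global Plaque Score. Recompute the t statistic.
5. State the time unit of the implant slopes, and base the implant plaque conclusion on the Day 90 implant-site values.

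The cost is a short rerun on existing data and a few reworded lines. No new data are needed.

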Figure 4. Interaction plot showing that group assignment interacted with time on the measure plaque.

[figure not shown]

Figure 5. Boxplots of plaque measures comparing treatment control group (Group A) and test group (Group X) for GPS. Test group (Group X) started with higher levels of plaque. Plaque decreased more in the test group (Group X) than in the control group (Group A), though both decreased significantly.

An analysis of covariance (ANCOVA) with the first visit as covariate was used to statistically control for the difference in average plaque scores at intake. ANCOVA results confirmed that test group (Group X) produced a significantly lower GPS measures (ANCOVA $F = 34.82$, $df = 1$, $p < 0.0001$), even with significant differences in the initial scores.

To further explore and confirm control rinse (rinse A) and test rinse (rinse X) treatment effects on plaque measurement, from Time 1 to Time 3, both a Student's t-test and a Bayesian analysis of group means were employed. The Bayesian analysis supported the ANCOVA results.

Another t-test showed test group's (Group X) GPS absolute change and rate of change were significantly greater than for control group (Group A): -1.43 versus 0.365, respectively. This difference is considered a large effect size, Cohen's $d = 2.21$ ($t = 8.35$, $df = 1$, $p < 0.0001$). Thus, the changes and rates of change for GPS were greater for the test group (Group X) than the control group (Group A).

Global Gingival Index Score

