Table 7. Summary table of differential effects of control Treatment (rinse A) and test Treatment (rinse X) across implant status and group assignment. The group by implant interaction is significant, indicating the mouthwashes acted differently on implant versus non-implant sites.

Tests of Between-Subjects Effects						
Plaque						
Source	Type III Sum of Squares	df	Mean Square	F	Sig.	
Intercept	1596.963	1	1596.963	3282.732	0.000	
implant	0.547	1	0.547	1.124	0.292	

group	1.108	1	1.108	2.278	0.134
implant * group	7.532	1	7.532	15.483	0.000
Error	49.62	102	0.486		

Both implant and non-implant sites in the test group (Group X) improved significantly more than control group (Group A), but the implant sites improved significantly more for test group (Group X) (Control group (Group A) slope = -0.151, Test Group (Group X) slope = -0.463, one-analysis of variance $p < 0.001$), a 207% reduction in plaque scores over control group (Group A). Thus, test group (Group X) plaque measures on implant sites improved by 57% more than on non-implant sites. See Figure 10.

[figure not shown]

Figure 10. Significant differential effects of mouthwashes on plaque at implant sites. Both groups showed significant decreases in plaque, but test group (Group X) showed significantly greater decrease when testing the difference in slopes.

Conclusions

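### The 57% larger plaque improvement at implants than at teeth cannot be reproduced, the document's own figures disagree on its direction, and no reported test supports a preferential plaque effect at implants

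*Combined protocol and SAP*

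**What the plan says.** Under Implants and Plaque, after Table 7, the document prints two plaque slopes for implant sites: "Control group (Group A) slope = -0.151, Test Group (Group X) slope = -0.463, one-analysis of variance", with p < 0.001. It calls the gap "a 207% reduction in plaque scores over control group (Group A"), and then says, as a consequence, that test-group "plaque measures on implant sites improved by 57% more than on non-implant sites". The caption of Table 7 reads its group-by-implant interaction as "indicating the mouthwashes acted differently on implant versus non-implant sites".

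The only definition of a slope is in Global Score Analyses: "These outcomes are measured as individual slopes of responses across the three observation visits". For whole-mouth plaque, Global Plaque Score gives the baseline: "The test group's (Group X) initial average GPS was 3.00 (SEM = 0.071) versus 2.35 (0.097"). At the last visit it gives the test group's "GPS (1.57, SEM = 0.110) was significantly lower" than the control value of 1.98. The changes are printed as minus "1.43 versus 0.365, respectively". The control figure is a fall too (2.35 to 1.98), printed without its minus sign.

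The text before Table 7 gives a further pair of plaque changes, -0.799 (test) and -0.156 (control), said to cover both implant and non-implant sites, with no unit. The Conclusions claim a preferential benefit at implant sites over non-implant sites, with improvement both larger and faster at p < 0.001.

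**The concern.** Two slopes that compare arms at implants carry no information about teeth, so a comparison of implants with teeth cannot follow from them. The document prints no non-implant plaque slope that could fill the gap. A plaque score cannot fall by more than 100%, so the 207% cannot be what its label says. Table 7 is a between-subjects table without time. It compares levels, while the claim is about change.

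Implants are the disease site in this trial, and a preferential effect there is a headline product claim. If the plaque figures behind it are undefined and point in different directions, the plaque half of that claim has no support in the report.

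**Working it through.** **1. The 207%.** (0.463 - 0.151)/0.151 = 2.066, and 0.463/0.151 = 3.07. It reproduces as a relative difference in slopes. The difference itself is 0.463 - 0.151 = 0.312. If the slopes are raw units per visit step, the fall in implant scores over two steps is 2 x 0.463 = 0.926 of a baseline of 2.84, or 33%. In the control arm it is 2 x 0.151 = 0.302 of 2.77, or 11%.

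**2. The 57%, on the raw per-visit scale.** The test whole-mouth slope is -1.43/2 = -0.715. Tables 2 and 3 confirm it. With an assumed split of 28 control and 29 test patients (57 in Table 3), the gap between arms is sqrt(4.019 x (1/28 + 1/29)) = 0.531, and the test slope is -0.4525 - 0.531 x 28/57 = -0.713. Splits from 27/30 to 30/27 give -0.70 to -0.73. The implant slope of -0.463 is therefore about 35% shallower than the whole mouth (0.463/0.715 = 0.65). For implants to be 57% steeper than teeth, the tooth slope would have to be -0.463/1.57 = -0.295.

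**3. Sign of the Table 7 interaction.** Table 4 is the combination of Tables 6 and 7: error 11.118 + 49.62 = 60.738, and implant-by-group 8.613 + 7.532 = 16.145 = 0.018 + 16.127. The averaged term is (sqrt(8.613) - sqrt(7.532))^2/2 = 0.018, so the gingival and plaque interactions have opposite signs. The same holds for implant (2.916) and group (1.954). In Table 1 all three gingival contrasts are positive (implants above teeth, test above control, interaction 0.81 - 0.19). Assuming those signs hold on average over visits, all three plaque contrasts are negative.

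**4. Plaque levels implied by Table 7.** Error df of 102 = 2 x 53 - 4 matches the 27 + 26 patients in Table 1. With three visits and harmonic mean cell size n = 4/(2/27 + 2/26) = 26.49, 3n = 79.47:
- grand mean = sqrt(1596.963/(4 x 79.47)) = 2.241
- group contrast = sqrt(1.108/79.47) = 0.118
- implant contrast = sqrt(0.547/79.47) = 0.083
- interaction contrast = sqrt(4 x 7.532/79.47) = 0.616

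| Cell | Table 1 baseline | Mean over visits | Fall |
|---|---|---|---|
| Test implants | 2.84 | 1.987 | 0.85 |
| Test teeth | 2.99 | 2.378 | 0.61 |
| Control implants | 2.77 | 2.413 | 0.36 |
| Control teeth | 2.32 | 2.188 | 0.13 |

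Here test-arm implants fall more than teeth, the opposite direction to step 2. The treatment effect is 0.853 - 0.357 = 0.50 at implants and 0.612 - 0.132 = 0.48 at teeth. Implants fall more than teeth under placebo as well.

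**5. Baseline against Table 7.** The baseline interaction contrast is (2.84 - 2.99) - (2.77 - 2.32) = -0.60. The visit-averaged contrast is -0.616. The significant interaction (F = 7.532/(49.62/102) = 15.48, which reproduces) is therefore almost all baseline imbalance, with about 0.016 left for a site-specific rinse effect.

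**6. The -0.799 and -0.156.** With no unit stated, they match neither the implant slopes (-0.463, -0.151), nor the whole-mouth slopes (about -0.71, -0.18), nor the falls in step 4. Their t-test has 55 df (57 patients), not the 53 patients of Table 7.

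**The case against.** The best defence is that the implant slopes may be log-scale coefficients. Data Management and Statistical Analysis says a gamma log link was used for most tests. The check is simple. A raw linear decline from the Table 1 baselines predicts visit-averaged implant means of 2.84 - 0.463 = 2.377 and 2.77 - 0.151 = 2.619, while Table 7 implies 1.987 and 2.413. An exponential decline predicts 1.917 and 2.400, which is closer. Solved backwards, Tables 1 and 7 give log slopes of -0.413 and -0.250 for test implants and teeth, and -0.145 and -0.060 for control. Test implants would then be about 1.66 times as fast as teeth, in the claimed direction and near 57%. The treatment effect would be 0.413 - 0.145 = 0.268 at implants and 0.250 - 0.060 = 0.190 at teeth, so the near-equality of 0.50 and 0.48 holds on the raw scale only. This stands as a possible reading. But the document does not say these slopes are on a log scale, the 57% is still not reproduced, and no site-by-time-by-group test of plaque is reported on either scale.

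A reader might infer the reverse: that implants improved about 37% less than teeth and that 57% is the ratio turned upside down. With 20 to 28 teeth and 1.45 implants per patient (assumed), the whole-mouth slope does imply a tooth slope near -0.73, and 0.73/0.463 is about 1.57. The documents do not support that conclusion. It mixes 57-patient whole-mouth data with a 53-patient implant analysis, and it assumes a shared raw scale. The whole-mouth data also contain zero scores (Table 3 minima of 0 at times 2 and 3). If three test patients with slopes near -1.50 (half the baseline of 3.00, an assumption) are removed, the whole-mouth slope becomes (29 x 0.713 - 3 x 1.50)/26 = 0.622 in size and the ratio drops to about 1.37. Tables 1 and 7 point the other way.

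It is also fair that the 207% is sound arithmetic under a wrong label.

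**Conclusion.** The 57% figure is not reproducible and does not follow from the slopes it is drawn from. Which site type improved more in the test arm cannot be settled from the report: the raw-scale slopes point to less at implants (-0.463 against about -0.71 for the whole mouth), and Tables 1 and 7 point to more (0.85 against 0.61). The 207% is a relative slope difference. Table 7 cannot show that the rinses acted differently by site. It has no time term, it treats a patient's implant and tooth scores as independent (102 error df from 53 patients), and its contrast of 0.616 is nearly the baseline 0.60.

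The Table 7 results assume three visits, cell sizes of 27 and 26, Table 1 baselines from the same patients, and gingival signs that persist from baseline. They carry no confidence interval. The plaque part of the preferential-implant conclusion is unsupported as reported, which is not the same as shown false. The difference between arms in plaque and the separate gingival index claim at implants are not refuted by this point.

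**What to change.** - State the scale and time unit of every slope and change score, including -0.463/-0.151 and -0.799/-0.156, and reconcile them with source data.
- Recompute plaque change at implants and at teeth, by arm, with confidence intervals, from one dataset and one patient set. Say how zero scores are handled.
- Report a time by implant by group test for plaque, in a model that accounts for implant and tooth scores from the same patient.
- Replace the 207% wording with the slope difference in its unit and a confidence interval (-0.312 per visit step, if the raw scale is confirmed).
- Correct the Table 7 caption to say that it compares levels averaged over visits.
- Delete the 57% statement and the plaque part of the preferential-implant conclusion unless the new test supports them.

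The cost is a re-analysis of existing data and text changes. No new data are needed.
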